# 8.7 Dosage modifications

# Aspirin

Aspirin dose cannot be modified, only stopped.

Patients will be made aware that aspirin should be used with caution before surgery, including tooth extraction. Temporary discontinuation of treatment may be necessary.

Participants that experience any aspirin-related severe toxicity (defined as ≥grade 3 Common Terminology Criteria for Adverse Events (CTCAE v5)) or significant gastrointestinal bleeding (grade 3 and 4), active gastrointestinal ulceration, new cases or worsening tinnitus (grade 2 or above), intracranial bleeding or hypersensitivity to aspirin should permanently discontinue aspirin immediately.

IRAS: 1005142 Page **61** of **109** 

COLO-PREVENT Protocol 11/12/2024: Version 4.0

#### **Metformin**

#### Run-in

Undesirable effects of metformin are most frequent during initiation of therapy and usually resolve spontaneously. To prevent them, it is recommended that metformin is taken during or after meals. Metformin does not cause hypo-glycaemia in non-diabetic patients and participants will be reassured about this prior to dosing. Participants will have a run-in period of 4 weeks at the once daily 500 mg metformin dose to allow time for gastrointestinal tolerance. If more than 80% of the prescribed dose is taken during this time, the research team will instruct the participant to increase their dose to twice daily 500 mg metformin tablets.

If the patient does not tolerate the 500 mg metformin then it is possible for the patient to have another 4 week run-in period using a MR formulation 500 mg dose. If this is deemed tolerable then patients will increase their dose to twice daily 500 mg MR release metformin tablets. If the participant is unable to tolerate the lowest dose of metformin then they can continue on the trial with aspirin alone.

#### Main trial

It is advised that metformin treatment will be paused for approximately 72 hours around the time of contrast-enhanced CT scans.

Metformin must be discontinued at the time of surgery under general, spinal or epidural anesthesia. Therapy may be restarted no earlier than 48 hours following surgery or resumption of oral nutrition and provided that renal function has been re-evaluated and found to be stable.

Metformin must be permanently discontinued in patients where the GFR < 30mls/min. Patients who develop acute and unstable heart failure, while on the study should discontinue metformin.

For patients who wish to stop metformin due to adverse events then they should be offered a trial of twice daily 500 mg MR formulation to improve tolerability. If adverse events persist then the metformin dose can be reduced to 500 mg once per day. No further dose modifications are permitted and therefore if adverse events continue the metformin should be permanently discontinued.

If a participant misses >20% of doses for aspirin in combination with metformin or aspirin alone, then it is at the discretion of site investigators as to whether it is appropriate to restart trial treatment.

#### 8.8 Known drug reactions and interaction with other therapies

The most common (>1/100 to <1/10) side effects of aspirin are increased bleeding tendencies and dyspepsia.

The most common (>1/100 to <1/10) side effects of metformin are taste disturbance and gastrointestinal disorders such as nausea, vomiting, diarrhoea, abdominal pain and loss of appetite.

IRAS: 1005142 Page **62** of **109** 

For the full list of undesirable effects please refer to sections 4.8 of the regulatory approved Summary of Product Characteristics (SMPCs) for aspirin and metformin provided in the Investigator and Pharmacy Site Files (ISF and PSF).

#### 8.9 Concomitant medication

#### **Permitted Medication**

Participants should be encouraged to take any regular medication throughout the trial unless they are not permitted (see below). All non-contraindicated medications that the responsible clinician feels are appropriate, for example, PPI, paracetamol and remedies for cough and colds, are allowed in the trial. If a patient develops diabetes while on the study they can remain on the study providing they continue to take metformin as part of their hypoglycaemic regimen.

The potential for interaction of trial treatments with all medicines should be checked against the information provided by the BNF (www.bnf.org) or local equivalent. Information on concomitant medication that has potential anti-cancer activity will be collected at each follow-up visit and call.

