# Exclusion criteria for the main trial but not the resveratrol Signal-Seeking trial:

- Methotrexate use
- Regular (>3 doses per week) prescribed or 'over the counter' (OTC) aspirin or regular (>3 doses per week) prescribed or OTC non-aspirin NSAID use
- Allergic or intolerant to ibuprofen or naproxen, metformin, aspirin or salicylate.
- Diabetic patients on drug treatment
- Current or previous treatment with metformin
- Known history of peptic ulcer disease
- Known history of lactic acidosis or predisposing conditions
- Prior use of NSAIDs is not an exclusion if they are self-prescribed and the patient is willing to stop use for the duration of the trial
- Use of long-term systemic corticosteroids

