#### 7.10 Withdrawal criteria

Every effort should be made by the research team to keep the participants in the trial. However, participants have the right to withdraw their consent to take part in the trial at any time without having to give a reason and this will not affect their future care. Withdrawal of consent details and reasons (if known) should be recorded on the CRF and in the medical notes.

In the unlikely event that a trial participant becomes pregnant during the study, trial treatment will be discontinued. Please refer to section 10.5 for guidance on pregnancy reporting.

The investigator may discontinue treatment of a participant at any time if they are not compliant with the trial protocol or to protect the participant's safety and well-being after consultation with the CI. The IMP may also be discontinued in the case of an adverse event which the investigator considers sufficient to jeopardise the safety of the participant. Participants who discontinue treatment, for whatever reason, will be encouraged to remain in the trial for collection of important outcome and safety data. These treatment ceased participants will be asked to continue attending visits for collection of data and samples. Participants not wishing to attend all subsequent visits, will be asked for their permission to collect data and samples at their exit surveillance colonoscopy. Additionally, some trial assessments (e.g. Food Frequency Questionnaire) may be collected over the telephone if the participant agrees to be contacted. As a minimum, important outcome and safety data will be collected remotely from the participant's medical record. Those declining this will be withdrawn from the trial (thus withdrawing their consent).

Withdrawals from the trial should be discussed with the CI or their deputy and the Trial Manager. If a participant has withdrawn/discontinued from the trial for any reason, then his/her screening and trial ID number(s) cannot be issued to another participant.

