#### Permitted medications

The guidance for permitted medications is as per the main trial; see section 8.9.

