For the main trial the primary analysis aims to show whether the combination of aspirin with metformin leads to clinically meaningful reduction in the MPP as compared to aspirin alone. Data from the aspirin arms of the SeAFOod trial (12) and 1st surveillance in the BCSP (2006 -2016, 1 year MPP for high risk patients and 3 year MPP for intermediate risk patients) have been provided ([name], personal communication). Assuming a MPP at 3 years in the untreated population of 1.2 polyps, this leads to a control MPP of 0.94 in the standard of care arm, after accounting for a 22% reduction in total MPP due to aspirin use, based on the SeAFOod data (12). This trial is powered to detect a reduction of 30% (0.66 vs 0.94) in the MPP of the combination arm, relative to aspirin alone. We estimate a sample size of 646 (323 per arm) would have 80% power at the 2-sided significance level of 5%. Allowing for 15% dropout at 3 years and crossover of 3% in each arm, the target sample size has been inflated to  $646/0.85 = 760^{\circ} - 1.13 = 862$  (431 per arm) individuals who will be randomised equally (1:1 ratio) to each treatment arm, with minimisation for BCSP Centre. We have predicted the dropout rate based on the 10% value reported for the one-year seAFOod trial (12) and have increased this figure to 15% due to the longer intervention period in COLOPREVENT; this rate is in line with previous aspirin polyp prevention trials that involved a ≥3 year follow-up (10). Crossover accounts for participants who have to stop taking metformin completely due to side effects, and also patients who are diagnosed with T2DM during the course of the trial and are prescribed metformin. Assuming a conservative but realistic acceptance and eligibility of 30% for the trial, a total of ~3200 high risk individuals need to be identified at screening colonoscopy.

IRAS: 1005142 Page **77** of **109** 

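### Section 8.9 ties remaining on the study after new diabetes to continued metformin, which does not fit the aspirin-alone arm and conflicts with the protocol's own retention and ITT rules

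*Protocol*

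**What the plan says.** Section 8.9 (Permitted Medication) deals with participants who develop diabetes while on the study: "they can remain on the study providing they continue to take metformin as part of their hypoglycaemic regimen". It applies to no particular arm.

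Other sections bear on the same participants:

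- **6.2** excludes from the main trial anyone with "Current or previous treatment with metformin", and also "Diabetic patients on drug treatment". Diabetes managed without drugs is not excluded.
- **8.7** lets a combination-arm participant who cannot tolerate the lowest metformin dose stay on the trial taking aspirin only. It also lists circumstances in which metformin must be stopped for good.
- **8.9**, in its closing part on drugs that are not permitted but become indicated, has the participant stop trial drug but encourages them to stay for outcome and safety data.
- **7.10** says: "Participants who discontinue treatment, for whatever reason, will be encouraged to remain in the trial for collection of important outcome and safety data". For those who will not attend visits: "As a minimum, important outcome and safety data will be collected remotely from the participant's medical record".
- **11.1** includes in its 3% crossover allowance per arm "patients who are diagnosed with T2DM during the course of the trial and are prescribed metformin".
- **11.3** analyses participants in the arm to which they were randomised.
- **9.9** brings the rule into the sub-trial: "The guidance for permitted medications is as per the main trial; see section 8.9".

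**The concern.** The sentence makes staying on the study depend on taking the drug that is randomised in the main trial. A combination-arm participant on trial metformin already meets the condition. An aspirin-alone participant has no metformin to continue, and must either start it or, read literally, leave. A condition applied after randomisation that one arm meets by default and the other does not can produce missing outcomes that differ by arm. The main trial is open-label, so sites will know which arm they are applying it to.

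Sites will need this instruction. The main trial measures glucose and HbA1c at weeks 0, 25, 52, 78, 104 and 154, so new diabetes will be detected during follow-up. Those affected would not be a random subset: section 2.3 hypothesises that people in poor metabolic health may benefit more. An outcome that was never collected cannot be recovered at analysis.

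**Working it through.** **1. Setting the sections side by side.**

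| Participant with new diabetes | 8.9, read literally | Other sections |
|---|---|---|
| Combination arm, on metformin | stays | stays |
| Combination arm, metformin stopped under 8.7 | does not stay | 8.7: an intolerant participant stays on aspirin; 7.10: stays for outcome data |
| Aspirin alone, prescribed metformin | stays, if starting counts as continuing | 11.1: counted as crossover |
| Aspirin alone, not prescribed metformin | does not stay | 7.10 and 11.3: followed up and analysed as randomised |
| Sub-trial, not on metformin | does not stay | 7.10: followed up |

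The fourth row carries the statistical risk. Section 11.1 does not mention this group. A further oddity is that a person with diet-controlled diabetes may enter under 6.2 and sit in the aspirin-alone arm without metformin, while a person whose diet-controlled diabetes begins after randomisation fails the condition.

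**2. Reproducing the planned sample size.** Inputs from 11.1: MPP 0.94 against 0.66, over-dispersion 2.0, two-sided 5%, 80% power. Taking variance as twice the mean:

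n per arm = (1.960 + 0.842)² × 2 × (1/0.94 + 1/0.66) / ln(0.94/0.66)² = 323.7

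This matches the stated 323 per arm (646). For the inflation, 646/0.85 = 760 and 760 × 1.13 = 858.8, within 0.5% of the stated 862 (431 per arm). No stated figure depends on the 8.9 rule.

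**3. Power cost of a one-sided loss (illustration).** After 15% dropout, 431 × 0.85 = 366 per arm are evaluable. Power = Φ(ln(0.94/0.66)/SE − 1.96), with SE² = 2/(0.94 n₁) + 2/(0.66 n₂). Before crossover dilution:

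| Further loss, aspirin-alone arm only | Participants of 431 | Power |
|---|---|---|
| none | 0 | 84.6% |
| 1% | 4 | 84.4% |
| 3% | 13 | 84.1% |
| 5% | 22 | 83.7% |
| 10% | 43 | 82.7% |

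The 3% row is the same number as the crossover allowance in 11.1 (0.03 × 431 = 12.9). That allowance also covers people who stop metformin, so it is not an estimate of diabetes incidence.

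**4. Possible bias (assumed inputs, none in the protocol).** If a fraction p of the aspirin-alone arm is lost and those people have r times the average MPP, the observed control mean is multiplied by (1 − rp)/(1 − p).

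- r = 1: factor 1, no shift.
- r = 1.5, p = 1.5% (6 of 431): 0.9775/0.985 = 0.992.
- r = 1.5, p = 3% (13 of 431): 0.955/0.97 = 0.985.

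In the last case, with the combination arm unaffected, the apparent reduction changes from 1 − 0.66/0.94 = 29.8% to 1 − 0.66/(0.94 × 0.985) = 28.7%. Section 2.3 speaks of greater treatment benefit in poor metabolic health, not of a higher polyp count under control, so it does not support any particular r above 1.

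**The case against.** The strongest reply is that the protocol as a whole keeps these people. Section 7.10, which governs withdrawal, does not list new diabetes and sets a minimum of outcome collection from the medical record. The main-trial exit colonoscopy is a routine clinical procedure, so the primary outcome arises whether or not trial visits continue. Analysis is by ITT. A reader might infer from 8.9 that follow-up of aspirin-alone participants will be lost. The documents do not support that: loss requires a site to apply one ambiguous sentence literally, against 7.10.

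A reader might also infer that aspirin-alone participants cannot meet the condition, or that only one arm can. Section 11.1 expects some to be prescribed metformin after diagnosis and budgets for them as crossover, so that contamination is already planned for. Combination-arm participants who have stopped metformin would fail the literal test as well, which narrows the asymmetry.

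A third inference, that the sub-trial comparison is biased in the same way, also fails. No sub-trial arm supplies metformin, allocation is double-blind, and randomisation takes metformin use into account. Nor does the protocol say what share of sub-trial participants would be off metformin.

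All of this stands and limits the point. It does not remove the contradiction: 8.9 gives sites a condition that 7.10, 8.7 and 11.3 do not share. Elsewhere the protocol separates stopping drug from leaving the trial; this sentence does not.

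**Conclusion.** The point holds as an internal contradiction with a risk of differential missing outcomes, not as a planned exclusion. The 8.9 condition does not fit the aspirin-alone arm unless those participants start metformin, and it conflicts with 8.7, 7.10, the closing part of 8.9 and ITT. If sites follow it literally, the main trial could lose participants with new diabetes who are not on metformin, more often from the aspirin-alone arm.

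The size is unknown and probably small. Power falls by about half a point if 13 aspirin-alone participants are lost. The bias illustration, a control mean 0.8% to 1.5% too low, rests wholly on assumed incidence, metformin uptake and relative MPP, and should not be quoted as an estimate. In the sub-trial the condition is ill-fitting, without bias by arm. The point is still worth acting on, because the correction is nearly free and protects the randomised comparison.

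**What to change.** Reconcile 8.9 and 9.9 with 7.10, 8.7 and 11.1 by separating two questions:

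1. **Continuing trial treatment after new diabetes.** This is a clinical rule for the investigators to settle, stated for each arm of the main trial and for the sub-trial.
2. **Continuing in the trial.** State that new diabetes, however treated, does not end follow-up, the exit colonoscopy outcome or ITT inclusion in any arm of either trial.

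No new data collection is needed. Section 7.7 already records new and changed medication at every visit after baseline, so metformin starts in the aspirin-alone arm are captured and can feed the adherence or CACE analyses foreseen in 11.3 and 11.5. The cost is a sentence or two in 8.9 and 9.9 and a note to sites, with no change to the sample size.

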# **Not-permitted medication**

## **ASPIRIN**

Medications not permitted include anti-coagulant and anti-platelet medication, aspirin (including over the counter preparations) and others including methotrexate. See appendix I for a list. Regular NSAID use is not permitted. NSAIDs should be avoided wherever possible but short-term intermittent/occasional NSAID use is allowed (maximum of 2 consecutive weeks of regular use). Long-term systemic corticosteroids are not permitted but short-term intermittent use is allowed (maximum of two consecutive weeks). See appendix I for further details. Participants should be counselled about over the counter aspirin and NSAID use prior to consent and this should be reinforced at follow-up visits.

#### **METFORMIN**

Patients should be advised to avoid acute alcohol intoxication as this is associated with an increased risk of lactic acidosis.

#### Medication to be used with caution

#### **ASPIRIN**

Aspirin has the potential to interact with the following medications: Selective Serotonin Reuptake Inhibitors (SSRIs), Iloprost, kaolin, metoclopramide, phenytoin, probenecid, spironolactone, sulfinpyraxone, thiopental, valproate, venlafaxine and zafirlukast. See the BNF for further details and a full list of interactions.

#### **METFORMIN**

Intravascular administration of iodinated contrast media may lead to renal failure, resulting in metformin accumulation and an increased risk of lactic acidosis.

Some medicinal products can adversely affect renal function which may increase the risk of lactic acidosis, e.g. selective cyclo-oxygenase (COX) II inhibitors, ACE inhibitors, angiotensin II receptor antagonists and diuretics, especially loop diuretics.

Metformin is a substrate of both organic cation transporters OCT1 and OCT2. Precautions are advised when considering co-administration of metformin with inhibitors of OCT1 (such

IRAS: 1005142 Page **63** of **109** 

as verapamil), inducers of OCT1 (such as rifampicin), inhibitors of OCT2 (such as cimetidine, dolutegravir, ranolazine, trimethoprime, vandetanib, isavuconazole); inhibitors of both OCT1 and OCT2 (such as crizotinib, olaparib).

# MANAGEMENT WHERE A MEDICATION THAT IS NOT PERMITTED BECOMES INDICATED DURING THE TRIAL

We would not expect patients who require a medication that is not permitted in the trial (see appendix I) to be consented to COLO-PREVENT because this should have been identified during the eligibility screening. However there may be participants who develop a medical condition during the trial where a medication that is not permitted becomes clinically indicated. Examples include but are not limited to: anti-coagulation for the treatment of pulmonary embolism, deep vein thrombosis or atrial fibrillation and anti-platelet therapy for the management of cardiovascular events. The participant would need to cease trial drug in these circumstances but should be encouraged to remain in the trial for collection of important outcome and safety data.

#### 8.10 Trial restrictions

Eligibility criteria have been formulated so that individuals with an increased risk of serious toxicity from either aspirin or metformin are excluded. Details of any concomitant illness (any illness present at the start of the trial) should be recorded at trial entry. If a change influences the participant's eligibility to continue in the trial, the investigator must be informed.

There are no special dietary requirements or restrictions for COLO-PREVENT as this could adversely affect recruitment, compliance and retention. Blood glucose is amongst the measures being monitored at all out-patient visits for safety.

Regular use of aspirin may adversely affect a pregnancy and/or foetal development. Regular aspirin or metformin use whilst breast feeding can also cause complications in the neonate/infant and should be avoided.

Therefore, participants joining COLO-PREVENT should not be pregnant or lactating at trial entry and should be advised against becoming pregnant during the trial treatment period.

Male participants and their female partners of child bearing potential must use medically acceptable forms of contraception during the trial.

A woman is defined as being of childbearing potential (WOCBP), i.e. fertile, following menarche and until becoming post-menopausal, unless permanently sterile. Permanent sterilisation methods include hysterectomy, bilateral salpingectomy and bilateral oophorectomy. A postmenopausal state is defined as no menses for 12 months without an alternative medical cause.

Acceptable birth control methods include:

- progestogen-only oral hormonal contraception, where inhibition of ovulation is not the primary mode of action
- male or female condom with or without spermicide
- cap, diaphragm or sponge with spermicide

IRAS: 1005142 Page **64** of **109** 

- combined (estrogen and progestogen containing) hormonal contraception associated with inhibition of ovulation:
  - o oral
  - intravaginal
  - o transdermal
- progestogen-only hormonal contraception associated with inhibition of ovulation:
  - o oral
  - o injectable
  - o implantable
- intrauterine device (IUD)
- intrauterine hormone-releasing system (IUS)
- bilateral tubal occlusion
- vasectomised partner (provided that partner is the sole sexual partner of the WOCBP trial participant and that the vasectomised partner has received medical assessment of the surgical success)
- True abstinence: When this is in line with the preferred and usual lifestyle of the
  participant (defined as refraining from heterosexual intercourse during the entire
  period of risk associated with the trial treatments. Periodic abstinence (e.g.,
  calendar, ovulation, symptothermal, post-ovulation methods), declaration of
  abstinence for the duration of exposure to IMP, and withdrawal are not
  acceptable methods of contraception).

## 8.11 Assessment and compliance with treatment

Residual numbers of tablets will be recorded to assess adherence in the CRF, this will need to be completed by a member of the research team before returning to pharmacy.

